#### 9.7.2. Study Drug Storage

All study drug sent to the study centers must be stored under the conditions specified on the drug package label (15 – 30 °C / 59 – 86 °F) in a secure area accessible only to the Investigator and his/her designated staff. All study drugs should be stored and inventoried according to applicable government regulations and study procedures.

### 9.7.3. Study Drug Returns

Government regulations require that all investigational drug materials not used in clinical trials be returned before or at the completion of the study.

The Investigator will return the designated copies of the completed dispensing and inventory record.

### 9.7.4. Method of Assigning Study Medication to Patients

Study medication will be assigned to patients through a centralized Interactive Voice Response System (IVRS), as described in the IVRS user manual that will be provided to the sites. Sites will contact the IVRS to obtain the package number assignment(s) for patients at each scheduled study visit

Study personnel will select the study medication bottle(s) from their inventory that correspond to the package number(s) assigned by IVRS. Study personnel will complete the tear-off labels on the bottles, affix them to the Investigational Product Labels page found in the patient's paper source binder, and dispense the study medication (bottles) to the patient. At subsequent study visits, study personnel will follow the same procedures as described above, contacting the IVRS as instructed in the IVRS manual.

### 9.7.5. Discontinuation and Tapering of Study Medication

Patients who discontinue early from the open-label extension study will have their study medication tapered over a 3-week period, reducing their daily dose by one-third per week. After tapering has been completed, patients should return to the site immediately, and complete all assessments and evaluations scheduled for Visit 5, if patient discontinued early during the first year of the open-label extension study, complete all assessments and evaluations scheduled for Visit 8 if patient discontinued early during the second year of the open-label extension study, and complete all assessments and evaluations scheduled for Visit 11 if patient discontinued early during the third year of the open-label extension study, and complete all assessments and evaluations scheduled for Visit 14 if patient discontinued early during the fourth year of the open-label extension study (Refer to Study Flow Chart in Appendix A).

### 9.8. Assessment of Compliance

Patient compliance with the study drug dosing regimen will be assessed by counts of tablets remaining in the study medication bottles that are returned at each study visit. Compliance will be based on the medication the patient was scheduled to take for the days between study visits. In addition, information on the average total daily dose will be calculated, based on the number of tablets remaining or returned in each bottle.

Patients will be instructed to bring used and unused study medication bottles with them to each study visit for accountability purposes. Tablets from each bottle for each dose

strength (50 mg, 100 mg, 300 mg) will be counted and recorded to assess patient compliance and correct dosage taken. If a patient is deemed to be non-compliant with taking study medication, the patient should be counseled by the site. If the patient continues to be non-compliant, they should be withdrawn from the study.

Along with drug accountability logs, the CRF will capture the data which includes the prescribed dosage, dates of first dose and last dose, and the number of tablets returned from each bottle for each dose strength. The CRFs will also provide a classification in to poly- or monotherapy with retigabine.

## **9.9. Concomitant Therapy**

### **9.9.1. Permitted Concomitant Medications**

Patients will take the background AED as prescribed by their physician. If adverse events considered to be secondary to retigabine occur, the total daily dose could be reduced by 150 mg/day every week, at Investigator discretion, as long as the dose is within 600-1200 mg/day. The background AED therapy can be adjusted if a patient develops adverse events similar to the previously experienced reaction to that AED.

After patients enter the open-label extension study, the Investigator will be allowed to adjust background AEDs, as clinically indicated. As needed, the background AED therapy can be adjusted to achieve the best efficacy/safety ratio, per Investigator discretion. If necessary, in the Investigator judgment, all background AEDs can be discontinued to achieve monotherapy with retigabine. The dose and reason to use a concomitant medication shall be recorded in the CRFs.

### **9.9.2. Prohibited Medications**

Use of felbamate and vigabatrin are prohibited. Concurrent use of any AEDs, or of any drug that could interfere with the absorption or metabolism of retigabine and background AED is also prohibited. Medications known to lower seizures (e.g. neuroleptics) and monoamine oxidase inhibitors (MAOIs) are not allowed.

## **9.10. Protocol Violations and Deviations**

A deviation from the protocol is an unintended and/or unanticipated departure from the procedures and/or processes approved by the Sponsor and the IRB/IEC/REB and agreed to by the Investigator. Deviations usually have an impact on individual patients or a small group of patients. A protocol violation occurs when there is non-adherence to the protocol that results in a significant, additional risk to the patient, when the patient or Investigator has failed to adhere to critical protocol requirements (inclusion/exclusion criteria) and the patient was enrolled without prior Sponsor approval, or when there is non-adherence to FDA regulations and/or ICH GCP guidelines.

The Investigator or designee must document and explain any deviation or violation from the approved protocol. The Investigator may implement a deviation from, or a change of the protocol to eliminate an immediate hazard to study patients without prior IRB/IEC/REB approval. Immediately after the implemented deviation, violation or change to eliminate the immediate hazard to the study patient(s), the Investigator must submit a report explaining the reasons for the protocol deviation, violation or change to the Sponsor. If required, the regulatory authorities will be notified. The appropriate IRB/IEC/REB will be notified of specified, critical violations or violations that place patients at added, significant risk.

Protocol violations and deviations will be documented by the clinical monitor throughout the course of the monitoring visits. Investigators will be notified of violations and deviations and/or in writing by the monitor, and the Principal Investigator will be required to identify corrective action to eliminate future violations and deviations.

## 10. STUDY PROCEDURES

### 10.1. Study Flow Chart

As presented in the Study Flow Chart (see Appendix A), Study Visit 1 will have a window range of  $\pm 3$  days. After Study Visit 1, all remaining study visits will have a window range of  $\pm 7$  days around that visit day to accommodate individual schedules, as follows:

- Baseline for the open-label extension study corresponds to the assessments performed at the last visit of the Maintenance phase (Visit 9) of Study VRX-RET-E22-302 for all patients. The final, baseline eligibility assessment for the open-label extension study, including obtaining informed consent and dispensing open-label study medication will be performed at the last visit of the Transition phase (Visit 11) of Study VRX-RET-E22-302.
- Study Visit 1 (at Month 1  $\pm 3$  days)
- Study Visit 1a for Hematological Monitoring (at Month 2  $\pm 7$  days)
- Study Visit 2 (at Month 3  $\pm 7$  days)
- Study Visit 2a for Hematological Monitoring (at Month 4  $\pm 7$  days)
- Study Visit 3 (at Month 6  $\pm 7$  days)
- Study Visit 3a for Hematological Monitoring (at Month 8  $\pm 7$  days)
- Study Visit 4 (at Month 9  $\pm 7$  days)
- Study Visit 4a for Hematological Monitoring (at Month 10  $\pm 7$  days)

- Study Visit 5 (at Month 12  $\pm$ 7 days).
- Study Visit 6 (at Month 16  $\pm$ 7 days)
- Study Visit 7 (at Month 20  $\pm$ 7 days).
- Study Visit 8 (at Month 24  $\pm$ 7 days).
- Study Visit 9 (at Month 28  $\pm$ 7 days).
- Study Visit 10 (at Month 32  $\pm$ 7 days).
- Study Visit 11 (at Month 36  $\pm$ 7 days).
- Study Visit 12 (at Month 40  $\pm$ 7 days).
- Study Visit 13 (at Month 44  $\pm$ 7 days).
- Study Visit 14 (at Month 48  $\pm$ 7 days).

Each study month will be defined as 30 calendar days. If a patient visit occurs outside the visit window, the study clinical monitor (CRA) should be notified and the reason for the deviation noted. An attempt should be made to ensure that the patient returns for subsequent visits on schedule using the last visit of the Transition phase (Visit 11) of Study VRX-RET-E22-302, which corresponds to the final, baseline eligibility visit for the open-label extension study.

## **10.2. Efficacy Assessments**

Patients will keep a seizure diary throughout the study. The anticonvulsant efficacy of retigabine will be evaluated by comparison of baseline seizure frequency (obtained during the 8-week baseline period of Study VRX-RET-E22-302) with seizure frequency obtained during retigabine therapy in this open-label extension study (VRX-RET-E22-304). The primary efficacy variable is the percentage change in the monthly seizure rate from the baseline phase to the open-label treatment phase. The proportion of responders (patients experiencing  $\geq$  50% reduction in seizure frequency) from baseline to the open-label treatment phase will also be evaluated.

## **10.3. Safety Assessments**

Safety assessments will be evaluated, based on reports of AEs and results of vital signs (supine and standing blood pressure, pulse, and temperature), weight, clinical laboratory evaluations (blood chemistries, hematology and urinalysis including microscopy), a 12-lead ECG, and physical and neurological examinations. Post-void residual (PVR) bladder ultrasounds to assess urinary retention and the American Urological Association (AUA) Symptom Index to assess urinary voiding function will also be performed during the first, second, third and fourth year of the open-label extension study.

Clinical evaluations specific to hematology will be obtained on patients on a monthly basis for approximately 4 months and then every two months for the next 6 months. (See Appendix A for Study Flow Chart.)

### **10.3.1. Vital Sign Measurements and Weight**

Complete vital sign measurements (including supine and standing blood pressure, heart rate, and temperature) will be obtained throughout the study at all visits. Evaluations of blood pressure and heart rate will be performed supine at each study visit, and again after the patient has been standing for approximately 2 minutes.

Weight [pounds (lb) or kilograms (kg)] will also be measured in ordinary indoor clothing (without shoes) and will be recorded at all study visits

Abnormal vital sign values that are deemed clinically significant by the Investigator will be reported as AEs in the study CRF.

### **10.3.2. Physical and Neurological Examinations**

A complete physical and neurological examination will be performed annually at Visit 5, Visit 8, 11 and Visit 14. Brief neurological examinations will be performed at all other study visits, including visits 1, 2, 3, 4, 6, 7, 9, 10, 12 and 13.

### **10.3.3. Electrocardiograms**

A 12-lead ECG will be performed at all study visits during the first year of the open-label extension study (Visits 1, 2, 3, 4, 5), and annually at Visits 8, 11 and 14. The ECG parameters that will be assessed are heart rate, PR interval, QRS interval, QT interval, and QTc interval. All ECG tracings will be sent to Quintiles ECG Services for central reading. Quintiles ECG Services will provide a central ECG analysis and transmit a feedback of preliminary results via facsimile to the investigation site within 24 hours. Trained technicians will read all ECGs manually, and any abnormal finding will then be over-read by board-certified cardiologists. QT intervals will be corrected using both Bazett's and Fridericia's formulas. For purposes of clinical study conduct, Bazett's QT correction will be used. For purposes of data analysis, Fridericia's QT correction will be considered as primary. Changes from baseline QTc interval will be monitored on an ongoing basis throughout this study.

Increases in Bazett's QTc interval of >60 msec from baseline or QTc interval of >500 msec anytime during the study should be confirmed on a repeat ECG. Any such occurrence shall result in notification of the Investigator and the study medical monitor for immediate review of the tracings and discussion with Valeant.

  - a. A urine pregnancy test will be performed at Visit 0 to immediately confirm non-pregnancy eligibility for female patients of child-bearing potential.
  - b. A serum  $\beta$ -HCG pregnancy test for women of childbearing potential will be performed at Study Visit 5 and annually thereafter.
  - c. A pregnancy test should be performed during the study whenever a woman's menstrual period is 5 days late.
4. **Routine urinalysis:** specific gravity, pH, protein/albumin, glucose/sugar, ketones/acetone, and hemoglobin/blood. In order to standardize measurements, Bayer multistix 8-SG or equivalent dipsticks will be used.
5. **Microscopic urinalysis:** RBC, WBC, casts, and crystals/cells.

All laboratory tests with values that become abnormal after drug administration will be repeated as clinically indicated until the values return to normal, or until the etiology has been determined and the condition considered stable. Abnormal laboratory test results that are considered to be clinically important by the Investigator will be reported as an AE in the CRF. A laboratory abnormality will not be considered an AE unless:

- Intervention is required.
- Changes in dose of retigabine are required (decrease, discontinued, interrupted).
- Other treatment/therapy is required.
- Associated with other diagnoses

Laboratory results will be reported to the Investigator who will review abnormal laboratory findings for clinical significance. The Investigator will note any laboratory test results of clinical concern, or values that were outside normal ranges and provide details of the relationship to study drug and the action taken. If a change in a laboratory value represents a medical condition, the medical condition will be listed in the AE record. If no correlation is possible, the direction of change (increase or decrease) rather than the actual value will be recorded.

Laboratory results specific to neutrophil counts will be flagged in the laboratory reports if the absolute neutrophil counts are  $< 1.0 \times 10^3$ . For all such cases, the investigator shall report these results in an expedited manner, whether or not they are considered a serious event.

Note: For all serious hematological events or infections, the investigator shall report these in an expedited fashion, whether they are considered unexpected or not.

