- In addition to the scheduled pregnancy tests, a pregnancy test should be performed during the study whenever a woman's menstrual period is 5 days late.
- The AUA Symptom Index and the PVR bladder ultrasound will only be performed during the first, second, third, and fourth year of the open-label extension study (Visits 1, 2, 5, 8, 11, and 14).
- Dispensation of study medication is not applicable at the final study visit, if a patient has discontinued early or completed the open-label extension study.
- Study visits added per FDA comments that the open label extension trial should include more frequent hematological monitoring. These are now in-line with the hematological monitoring frequencies per the VRX-RET-E22-302, double-blind trial.

CONFIDENTIAL

RM2009/00475/00  
VRX-RET-E22-304

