## 4 STATISTICAL METHODS

### 4.1 Study Patients

#### 4.1.1 Disposition of Patients

Patients are free to discontinue their participation in the study at any time and without prejudice to further treatment at their local site. The Investigator must withdraw any patient from the study if that patient requests to be withdrawn. Patients withdrawn from the study will not be replaced, regardless of the reason for withdrawal. The patient's participation in this study may be discontinued due to the following reasons:

- Patient experiences an intolerable AE.
- Investigator decides patient has an “unsatisfactory response – efficacy.”
- Patient becomes pregnant.
- Patient is unwilling or unable to continue the study.
- Patient is non-compliant with study procedures.
- Patient needs medication not allowed in the protocol.
- Any clinically significant change in patient's medical condition.
- Persistent ALT or aspartate aminotransferase (AST) above 3 times the ULN; will be confirmed by repeating laboratory assessment within 1 week.
- ALT or AST levels are above 5 times the ULN at any time during the study.
- Confirmed QTc prolongation defined as QTc (Bazett's) >500 msec or an increase in QTc (Bazett's) of >60 msec from baseline.

- Investigator decides that withdrawal from the study is in the best interest of the patient.
- Request of the Sponsor.
- Hematological reasons or infections – for all such patients, the investigator shall report these in an expedited manner, whether or not they are considered serious or unexpected.

A summary of the number and percentage of discontinuations by primary reason will be provided together with descriptive statistics for the time until treatment discontinuation (days).

A by-patient listing of patient withdrawal/study completion details will also be provided.

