#### 4.5.4 Clinical Laboratory Evaluation

All clinical laboratory assessments are implemented by a central laboratory.

The clinical laboratory data were collected at baseline, Months 1, 3, 6, 9, 12, 16, 20, 24, 28, 32, and 36. Additional hematological assessments are collected at Months 2, 4, 8 and 10.

The laboratory data include:

1. Hematology: hemoglobin, hematocrit, RBC count, WBC count with differential, and platelet count.
2. Blood chemistries: sodium, potassium, chloride, bicarbonate, glucose, cholesterol, creatinine, calcium, phosphorus, BUN, uric acid, total bilirubin, total protein, AST, ALT, and alkaline phosphatase levels.
3. Routine urinalysis: specific gravity, pH, protein/albumin, glucose/sugar, ketones/acetone, and hemoglobin/blood. In order to standardize measurements, Bayer multistix 8-SG or equivalent dipsticks will be used.
4. Microscopic urinalysis: RBC, WBC, casts, and crystals/cells.

Descriptive statistics for laboratory results and change from baseline for each visit will be presented separately for hematology, biochemistry and urinalysis parameters. The number of patients with clinically significant liver function tests will also be presented.

A by-patient listing of all laboratory data will also be provided with abnormal values highlighted, and including centre, patient identifier, age, sex, race, weight and visit. A listing of the central laboratory reference ranges will also be provided.

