**CONFIDENTIAL**

RM2009/00475/00  
VRX-RET-E22-304

Valeant Pharmaceuticals North America  
 Protocol Number: VRX-RET-E22-304

PAGE X OF X

TABLE 1 NUMBER (%) OF PATIENTS WHO DISCONTINUED TREATMENT DURING THERAPY PHASE BY PRIMARY REASON  
 SAFETY POPULATION

	RETIGABINE (N=XXX)
DISCONTINUED ANY REASON	xx (xx.x%)
ADVERSE EVENT	xx (xx.x%)
UNSATISFACTORY RESPONSE - EFFICACY	xx (xx.x%)
PREGNANT	xx (xx.x%)
UNWILLING OR UNABLE TO CONTINUE THE STUDY	xx (xx.x%)
NON-COMPLIANT WITH STUDY PROCEDURES	xx (xx.x%)
REQUIRES MEDICATION NOT ALLOWED IN THE PROTOCOL	xx (xx.x%)
CLINICALLY SIGNIFICANT CHANGE IN MEDICAL CONDITION	xx (xx.x%)
PERSISTENT ALT OR AST ABOVE 3xULN	xx (xx.x%)
ALT OR AST ABOVE 5xULN AT ANY TIME	xx (xx.x%)
CONFIRMED QTC PROLONGATION	xx (xx.x%)
INVESTIGATOR DECISION	xx (xx.x%)
SPONSOR REQUEST	xx (xx.x%)
FAILURE TO RETURN	xx (xx.x%)
PATIENT REQUEST UNRELATED TO STUDY	xx (xx.x%)
OTHER EVENT	xx (xx.x%)

32

CONFIDENTIAL

RM2009/00475/00  
 VRX-RET-E22-304

Program Path/sas program name

Run Date:

TABLE 2 TIME UNTIL TREATMENT DISCONTINUATION (DAYS) DESCRIPTIVE STATISTICS  
SAFETY POPULATION

STATISTICS	RETIGABINE (N=XXX)
N	xxx
MEAN	xxx.x
STD	xxx.xx
MEDIAN	xxx.x
MINIMUM	xxx
MAXIMUM	xxx

Valeant Pharmaceuticals North America  
 Protocol Number: VRX-RET-E22-304

PAGE X OF X

TABLE 3 DEMOGRAPHIC AND BASELINE CHARACTERISTICS  
 SAFETY POPULATION

STATISTICS	RETIGABINE (N=XXX)
AGE - YEAR	
N	xxx
MEAN	xxx.x
STD	xxx.xx
MEDIAN	xxx.x
MINIMUM	xxx
MAXIMUM	xxx
SEX - N (%)	
MALE	xxx (xx.x%)
FEMALE	xxx (xx.x%)
RACE - N (%)	
CAUCASIAN	xxx (xx.x%)
AFRICAN-AMERICAN (BLACK)	xxx (xx.x%)
HISPANIC	xxx (xx.x%)
ASIAN	xxx (xx.x%)
OTHER	xxx (xx.x%)
HEIGHT - CM	
N	xxx
MEAN	xxx.x
STD	xxx.xx
MEDIAN	xxx.x
MINIMUM	xxx
MAXIMUM	xxx
WEIGHT - KG	
N	xxx
MEAN	xxx.x
STD	xxx.xx
MEDIAN	xxx.x
MINIMUM	xxx
MAXIMUM	xxx

Program Path/sas program name

Run Date:

TABLE 3 DEMOGRAPHIC AND BASELINE CHARACTERISTICS  
SAFETY POPULATION

STATISTICS	RETIGABINE (N=XXX)
BMI - (KG/M^2)	
N	xxx
MEAN	xxx.x
STD	xxx.xx
MEDIAN	xxx.x
MINIMUM	xxx
MAXIMUM	xxx

35

CONFIDENTIAL

RM2009/00475/00  
VRX-RET-E22-304

Valeant Pharmaceuticals North America  
 Protocol Number: VRX-RET-E22-304

PAGE X OF X

TABLE 4 EPILEPSY HISTORY  
 SAFETY POPULATION

TYPE OF EPILEPSY STATISTICS	RETIGABINE (N=XXX)
PARTIAL (PRIMARY DIAGNOSIS)	
DURATION - YEARS	
N	xxx
MEAN	xxx.x
STD	xxx.xx
MEDIAN	xxx.x
MINIMUM	xxx
MAXIMUM	xxx
GENERALISED	
DURATION - YEARS	
N	xxx
MEAN	xxx.x
STD	xxx.xx
MEDIAN	xxx.x
MINIMUM	xxx
MAXIMUM	xxx

36

CONFIDENTIAL

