1ST SYSTEM ORGAN CLASS PREFERRED TERMS BELOW	xxx ( xx.x%) xxx ( xx.x%)
2ND SYSTEM ORGAN CLASS PREFERRED TERMS BELOW	xxx ( xx.x%) xxx ( xx.x%)

Valeant Pharmaceuticals North America  
 Protocol Number: VRX-RET-E22-304

PAGE X OF X

TABLE 16 NUMBER (%) OF PATIENTS REPORTING ADVERSE EVENTS BY MAXIMUM SEVERITY  
 SAFETY POPULATION

SYSTEM ORGAN CLASS PREFERRED TERM	RETIGABINE (N=XXX)		
	MILD	MODERATE	SEVERE
1ST SYSTEM ORGAN CLASS PREFERRED TERMS BELOW	xxx ( xx.x%)	xxx ( xx.x%)	xxx ( xx.x%)
2ND SYSTEM ORGAN CLASS PREFERRED TERMS BELOW	xxx ( xx.x%)	xxx ( xx.x%)	xxx ( xx.x%)

57

CONFIDENTIAL

RM2009/00475/00  
 VRX-RET-E22-304

Program Path/sas program name

Run Date:

Valeant Pharmaceuticals North America  
Protocol Number: VRX-RET-E22-304

PAGE X OF X

Use Template for TABLE 15 to produce:

TABLE 17 NUMBER (%) OF PATIENTS REPORTING TREATMENT-EMERGENT ADVERSE EVENTS AT LEAST POSSIBLY RELATED TO STUDY DRUG  
TABLE 18 NUMBER (%) OF PATIENTS REPORTING TREATMENT-EMERGENT ADVERSE EVENTS THAT LEAD TO DOSE MODIFICATION/INTERRUPTION  
TABLE 19 NUMBER (%) OF PATIENTS REPORTING FATAL TREATMENT-EMERGENT ADVERSE EVENTS  
TABLE 20 NUMBER (%) OF PATIENTS REPORTING SERIOUS TREATMENT-EMERGENT ADVERSE EVENTS  
TABLE 21 NUMBER (%) OF PATIENTS REPORTING ADVERSE EVENTS THAT CAUSED WITHDRAWAL FROM STUDY

Valeant Pharmaceuticals North America  
 Protocol Number: VRX-RET-E22-304

PAGE X OF X

TABLE 22 OBSERVED MEANS AND STANDARD DEVIATIONS OF LABORATORY TEST RESULTS AND CHANGE FROM BASELINE BY MONTH - SERUM CHEMISTRY SAFETY POPULATION

TEST NAME (TEST UNIT)	TIMEPOINT	n	RETIGABINE (N=XXX)		Change from Baseline Mean (STD)
			Mean	(STD)	
SODIUM (MMOL/L)	BASELINE	xxx	xx.x	(xx.xx)	
	MONTH 1	xxx	xx.x	(xx.xx)	xx.x (xx.xx)
	MONTH 3	xxx	xx.x	(xx.xx)	xx.x (xx.xx)
	MONTH 6	xxx	xx.x	(xx.xx)	xx.x (xx.xx)
	MONTH 9	xxx	xx.x	(xx.xx)	xx.x (xx.xx)
	MONTH 12	xxx	xx.x	(xx.xx)	xx.x (xx.xx)
	MONTH 16	xxx	xx.x	(xx.xx)	xx.x (xx.xx)
	MONTH 20	xxx	xx.x	(xx.xx)	xx.x (xx.xx)
	MONTH 24	xxx	xx.x	(xx.xx)	xx.x (xx.xx)
	MONTH 28	xxx	xx.x	(xx.xx)	xx.x (xx.xx)
	MONTH 32	xxx	xx.x	(xx.xx)	xx.x (xx.xx)
	MONTH 36	xxx	xx.x	(xx.xx)	xx.x (xx.xx)
POTASSIUM (MMOL/L)	:				

59

CONFIDENTIAL

Use Template for TABLE 22 to produce:

TABLE 24 OBSERVED MEANS AND STANDARD DEVIATIONS OF LABORATORY TEST RESULTS AND CHANGE FROM BASELINE BY MONTH - HEMATOLOGY  
 TABLE 25 OBSERVED MEANS AND STANDARD DEVIATIONS OF LABORATORY TEST RESULTS AND CHANGE FROM BASELINE BY MONTH - URINALYSIS

Program Path/sas program name

Run Date:

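### The hematology visits added on FDA comment and the protocol's neutrophil limit reach no summary table, only by-patient Listing 19, and Table 1 has no row for hematological withdrawals

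*Protocol*

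**What the plan says.** **Monitoring.** Protocol 10.3.4 states that neutrophil results "will be flagged in the laboratory reports if the absolute neutrophil counts are" below 1.0 x 10^3, and that the investigator must report every such case in an expedited manner, serious or not. Visits 1a, 2a, 3a and 4a (Months 2, 4, 8 and 10) exist only for hematology. The footnote in Protocol Appendix A explains them: "Study visits added per FDA comments that the open label extension trial should include more frequent hematological monitoring".

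**Analysis text.** SAP 4.5.4 acknowledges the extra samples: "Additional hematological assessments are collected at Months 2, 4, 8 and 10". It then commits to a summary: "Descriptive statistics for laboratory results and change from baseline for each visit will be presented separately for hematology, biochemistry and urinalysis parameters". SAP 4.3 sets the statistics for continuous data. If normally distributed, these are mean, SD, median, minimum, maximum and n. If skewed, they are quartiles with minimum, maximum and n.

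**Shells (SAP Section 10).** Under the Table 22 shell, which is worked through for sodium, the instruction "Use Template for TABLE 22 to produce" covers Table 24 (hematology) and Table 25 (urinalysis). The rows are baseline and Months 1, 3, 6, 9, 12, 16, 20, 24, 28, 32 and 36. The columns match the title, "OBSERVED MEANS AND STANDARD DEVIATIONS OF LABORATORY TEST RESULTS AND CHANGE FROM BASELINE BY MONTH": n, mean (SD), and mean (SD) of change.

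**Withdrawals.** The last of the 13 reasons in SAP 4.1.1 is "Hematological reasons or infections". The same section promises a count and percentage of discontinuations by primary reason. The shell for that summary (Table 1) carries the other reasons, for example "CLINICALLY SIGNIFICANT CHANGE IN MEDICAL CONDITION", but not this one.

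**The concern.** The primary objective is long-term safety and tolerability. A regulator asked for closer hematological monitoring, and the protocol responded with four extra visits, a numerical neutrophil limit and a named withdrawal reason. A reader of the report would expect to find how many patients fell below that limit, when, and how many left for that reason. As the shells stand, no summary table answers the first two questions, and the third has no count of its own.

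Severe neutropenia is a tail event. A mean and SD are poorly suited to showing one or two very low values, and the omitted months are exactly those added to look for them. If programmers follow the shells, the report would summarise hematology as though the added visits had not taken place.

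**Working it through.** The plan states no figure to reproduce; Protocol 11.3 gives sample size as not applicable. The check compares schedule, text and shells.

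**1. Time points.** Scheduled post-baseline hematology (SAP 4.5.4 and the SAP study flow chart): Months 1, 2, 3, 4, 6, 8, 9, 10, 12, 16, 20, 24, 28, 32, 36, which is 15. In the Table 22/24 shell: Months 1, 3, 6, 9, 12, 16, 20, 24, 28, 32, 36, which is 11.
- To Month 36: 15 - 11 = 4 missing, and 4/15 = 27%.
- In the first year: 9 scheduled, 5 shown, and 4/9 = 44% missing.

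The four missing months are 2, 4, 8 and 10. This is not a version lag. The SAP was written to Amendment 1, which introduced these visits, and the SAP's own flow chart shows them. The template suits chemistry, which is not sampled at those months, but not hematology.

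**2. Statistics.** SAP 4.3 requires a minimum and maximum whether the data are treated as normal or skewed. The Table 24 shell has neither. A minimum alone would reveal the lowest neutrophil count at each visit.

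**3. What a mean can show.** If one of n patients falls by d, the mean changes by d/n. The documents give neither d nor the number sampled per visit, so both are assumptions: d from 2 to 5 x 10^3, and n from 100 to 510 (510 is the stated ceiling on enrolment).

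| | n = 100 | n = 200 | n = 300 | n = 510 |
|---|---|---|---|---|
| d = 2 | 0.020 | 0.010 | 0.007 | 0.004 |
| d = 5 | 0.050 | 0.025 | 0.017 | 0.010 |

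The shell prints means to one decimal. The largest shift, 0.05, is half a unit in that last place. An isolated severe neutropenia could at most tip the rounding.

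**4. Threshold tables elsewhere.** Liver tests have one (Table 23), as do QTc (Tables 28 and 29), orthostatic hypotension (Table 32) and post-void residual volume (Table 41). Hematology has none, although the protocol supplies a limit.

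**5. Whether AE tables would catch a low count.** Under Protocol 10.3.4 a laboratory abnormality is not an AE unless it needs intervention, a change in retigabine dose or other therapy, or is associated with another diagnosis. SAP 4.5.2 joins its own conditions with an *and*, which read literally is narrower. A count below 1.0 x 10^3 that is watched without treatment or dose change can therefore be reported in an expedited manner and still appear in none of Tables 15 to 21.

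**6. Withdrawal rows.** Table 1 has 15 reason rows. Twelve match SAP 4.1.1. Three do not come from that list (failure to return, patient request unrelated to the study, other event). 12 + 3 = 15, and 13 - 12 = 1 reason without a row, the hematological one.

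**The case against.** The best defence is that the information is not lost. SAP 4.5.4 plans a listing of all laboratory data with abnormal values highlighted. The Listing 19 shell has visit, collection date, absolute neutrophils and high/low flags. The SAP text already covers every visit, and SAP 4.3 already calls for the minimum and maximum. On this view the fault is a chemistry shell reused without edits.

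For withdrawals, Protocol Section 12 makes a laboratory abnormality that leads to permanent discontinuation an AE, and infections are clinical events. Such cases would reach Table 21 by body system and preferred term, and Listing 14. Listing 1 gives each patient's primary and secondary reasons. Table 1 also has rows for adverse events and other events. Its rows may follow case report form codes, which are not among the documents.

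Most of this stands, and it rules out three stronger readings that a reader might be tempted to draw:
- *That the added monitoring yields nothing usable.* Listing 19 contradicts this.
- *That withdrawals for hematological reasons cannot be found in the planned tables.* Those recorded as AEs appear in Table 21.
- *That a known hematological signal prompted the visits.* The documents record only FDA comments asking for more frequent monitoring and expedited reporting, and alignment with the double-blind study. They describe no signal.

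The defence does not remove the gap. A listing gives no count, percentage or denominator. Its low flag is not stated to mean 1.0 x 10^3, so cases would have to be picked out by hand. Where text and shell disagree, the SAP does not say which governs. Table 21 spreads withdrawals over preferred terms and does not count the category that SAP 4.1.1 names. It is true that the protocol never promises a table of neutrophil counts below the limit; that part is an improvement rather than the correction of a contradiction.

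**Conclusion.** The point holds as a gap in the summary tables and a conflict between SAP text and shells. The four hematology visits added on FDA comment and the limit of 1.0 x 10^3 reach no summary table, only Listing 19. The Table 24 shell omits 4 of 15 post-baseline time points (4 of 9 in the first year) and shows no minimum or maximum, contrary to SAP 4.5.4 and 4.3. Table 1 covers 12 of the 13 reasons in SAP 4.1.1.

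The shift in the mean of about 0.004 to 0.05 is an illustration resting on the assumed falls and patient numbers. The conclusion does not depend on it, because a table of n and mean (SD) gives no count below a limit. The argument about AE tables concerns low counts that are neither treated nor followed by a dose change; how many there would be is unknown. The protocol states its limit without a volume unit, and I read it in the unit of Listing 19 (10^3 per microlitre).

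This is a moderate reporting weakness that should be corrected in a study whose primary objective is safety. Months 40 to 48 are also absent from the shell, because the SAP precedes the fourth year added by Amendment 2; that is a separate matter.

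**What to change.** 1. Give Table 24 its own shell with Months 2, 4, 8 and 10, and add minimum and maximum (with the median, to meet SAP 4.3).
2. Add a table of n (%) of patients with absolute neutrophils below 1.0 x 10^3, by visit and at any time after baseline. Use as denominator the patients with a count at that visit, or with at least one post-baseline count for the any-time row.
3. Add the missing hematological/infection row to Table 1. Derive it from the recorded withdrawal reason, or from the linked AE if the case report form has no such code, and state the rule in SAP 4.1.1.

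The cost is a few shell edits and one short table from central-laboratory data already collected. The Table 1 row may need a small derivation, depending on the case report form. No visit, sample or clinical rule changes.
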